Staff Referral: Referrals from primary care staff, including Primary Care Mental Health Integration (PCMHI), will provide our first-line recruitment source, as this will closely model how the patients would receive referrals in typical clinic care. We will make announcements about the study in multiple settings and forums (eg, announcements at team meetings, presentations at grand rounds). We will provide flyers and brochures to staff and discuss the study with them. We will ask primary care staff to provide potentially eligible Veterans (ie, positive on PTSD screen and without suicidal ideation, see detailed inclusion and exclusion criteria below) with brochures about the pilot study. If a Veteran demonstrates interest, primary care staff will either encourage Veteran to directly call study coordinator (information in brochure) or ask for permission to share their name and telephone number with the coordinator.

Self-Referral: To facilitate self-referral, we will use study fliers and brochures strategically placed in appropriate clinic locations and make announcements to inform primary care staff about the study. Individuals who are self-referred to the study will reach out to study staff to express their interest directly.

Active Outreach: Due to decreased in-person visits during the COVID pandemic (which limit opportunities for staff and self-referrals), we will identify potentially eligible Veterans who have a positive screen for PTSD in the past 2 months through an administrative data pull and recruit these Veterans through mailed letters and telephone calls. We will send out letters introducing the study and providing contact information for individuals to opt out of further contacts. Starting 10 days after the letter is sent, we will make up to 3 calls (on at least 2

different days) to provide more information about the study and conduct eligibility screening, for those who are interested.

3. Inclusion/Exclusion Criteria

To identify Veterans with PTSD symptoms and poor physical functioning who may benefit from the intervention, eligibility criteria are as follows (**Error! Reference source not found.**):

Inclusion: 1) ≥ 18 years old; 2) patient in primary care at MVAHCS; 3) score ≥ 3 on Primary Care PTSD Screen (PC-PTSD-5), which is routinely administered during primary care appointments (95% sensitivity and 85% specificity for PTSD diagnosis⁵⁵); 4) “yes” to any of 3 questions about health-related limitations from the Veterans RAND 36-Item Health Survey (VR-36),^{56, 57} as an indicator of impaired functioning; 5) has access to device (smart phone, tablet, or computer) that enables participation in videoconferencing; 6) has a smartphone or tablet that can support Garmin application; 7) has internet access for videoconferencing.

Exclusion: 1) active suicidal ideation or psychosis; 2) medical contraindication to participation (eg, complete paraplegia); 3) self-reported impairments in 2 or more activities of daily living (ADLs); 4) plans to move out of area permanently within next 4 months; 5) major neurocognitive impairment (e.g., dementia); 6) schizophrenia; 7) acute mental health crisis within the past 3 months (requiring an ED visit or hospitalization); and 8) routinely completing 150 minutes or more of moderate to vigorous activity per week. Individuals meeting these criteria may be unable to safely increase physical activity at home or not have a need for this program.

For Veterans referred by primary care and PCMHI staff, the study coordinator and/or principal investigator will conduct further eligibility screening using the following sources: 1) review of medical records for exclusion criteria (recent episodes of psychosis and medical contraindications to physical activity); 2) discussion with primary care provider for clarification about potential contraindications, as needed; and 3) telephone call to administer questions on mobility limitations, other health problems, and ADL impairments. For Veterans who self-refer, the study coordinator will first complete the PC-PTSD-5 and screening questions for suicidal ideation. After completing screening for eligibility, the study coordinator will schedule Veterans for a phone call to obtain informed consent and provide additional information on the intervention.

4. Informed Consent Procedures

The study coordinator will schedule a telephone call with Veterans to go over the informed consent form, HIPAA authorization form, and enrollment forms for financial incentives. We will also include other materials to describe the study (eg, FAQ document, expectations for confidentiality and privacy during group meetings, and troubleshooting Zoom). We will mail potential participants these materials ahead of the phone call, instructing them not to sign any forms until the call. During the call, the study coordinator will provide a thorough overview of study participation, risks, benefits, alternatives, protections, and IRB and study staff contact information. We will emphasize the voluntary nature of study participation and provide the opportunity for questions about the study. The consent process will be conducted by the study coordinator, who is trained in the ethics of human subject research. Those who agree to participate will mail back signed informed consent and HIPAA authorization forms via prepaid stamped envelopes. Signed informed consent and HIPAA authorization forms will be received by the study team before collection of any participant data.

5. Quantitative Data & Analyses (Table 4)

Feasibility will be quantitatively assessed as **recruitment** (proportion enrolled out of total identified as eligible), **attendance** (proportion who attend $\geq 75\%$ of in-person visits), and **retention** (proportion who complete post-intervention assessments). To determine feasibility, we will first evaluate recruitment and time needed to enroll participants. We anticipate approximately

20 Veterans per month may be eligible (based on preliminary data noted above), and with 20% recruitment, we expect to complete enrollment for each group in 4-6 weeks. We have set attendance and retention benchmarks at 75%, which are realistic estimates based on recent pilot studies of group exercise interventions for PTSD (participants attended an average of 78-82% of sessions and overall retention were 76-82%).^{25, 26}

Data on participant **physical activity** will be collected using both wearable devices and self-reported activity dairies. **Physical functioning** will be measured at baseline and post-intervention using VR-36, 6-minute walk,^{58, 59} and 30-second sit to stand.^{59, 60} Based on our clinical experience, these latter 2 tests can be feasibly administered to detect small but clinically relevant improvements in endurance and lower body strength. We will also assess **PTSD symptoms** (PTSD Checklist for DSM-5 [PCL-5])^{61, 62}; **depression** (Patient Health Questionnaire-9 [PHQ-9])⁶³; **pain** (brief 3-item scale on intensity and interference [PEG])⁶⁴; **fatigue** (PROMIS 4-item short form)⁶⁵; **sleep quality** (PROMIS sleep disturbance and impairment)^{66, 67}; **self-efficacy** (PROMIS general 4-item⁶⁸ and one item specific to physical activity); and **social support** for physical activity (1 item). We will compare physical activity data from wearable devices and self-reported diaries, for consistency and data quality for these different methods. For measures of physical functioning, PTSD and other symptoms, we will refine procedures for administering assessments and also confirm consistency and data quality.

Table 4. Assessments during Pilot Study.

	Baseline	During Intervention	Post-intervention
Feasibility & Acceptability			
Recruitment, Attendance & Retention		X	X
Acceptability of intervention components (semi-structured interviews)		X	X
Barriers & facilitators to attendance (semi-structured interviews)		X	
Physical Activity & Functioning			
Wearable device physical activity & sleep data		X	
Self-reported physical activity diaries	X	X	X
VR-36, 6-minute walk, 30-second sit to stand	X		X
Medical Conditions & Symptoms			
Medical diagnoses, medications (EMR)	X		
PTSD symptoms (PCL-5)	X		X
Depressive symptoms (PHQ-8)			
Pain (PEG)	X		X
Fatigue (PROMIS 4-item)	X		X
Sleep Disturbance & Impairment (PROMIS)	X		X
Self-efficacy	X		X
Social support for physical activity	X		X
EMR=Electronic Medical Record; PCL-5=PTSD Checklist for DSM-5; PEG=3-item scale on pain intensity and interference; PHQ-9=Patient Health Questionnaire-9; PROMIS=Patient Reported Outcomes Measurement Information System; PSQI=Pittsburgh Sleep Quality Index; VR-36=Veterans RAND 36 Item Health Survey			

6. Qualitative Data & Analyses (Table 4)

Qualitative assessments will involve semi-structured interviews at the end of month 2 and post-intervention, to address **acceptability** of intervention components, including session formats and topics and usability of wearable devices. Month 2 interviews will also elicit **barriers and facilitators** to attendance. Interviews will be audiorecorded and transcribed. We will use triangulation to integrate qualitative interview data with quantitative measures of attendance and retention. First, Drs. [name] and [name] will apply an established rapid approach for qualitative analysis to identify key themes.⁶⁹ This involves reviewing transcripts for the initial 3-4 interviews to develop templates that are then applied to summarizing subsequent transcripts. Summary information will be further reviewed and analyzed using matrices to identify major themes for each main topic (eg, acceptability of mHealth components). Then, a matrix will be

developed to compare themes for those who attended 75% of in-person visits with those who did not. A similar matrix will compare themes for those who completed post-intervention assessments and those who did not.

7. Withdrawal of Subjects

Participants can withdraw from the study at any point in time and for any reason by contacting study personnel in person, by telephone, or by mail, and requesting to withdraw. We anticipate termination of participation if:

1. The participant becomes ineligible to participate
2. The participant does not follow instructions from the researchers
3. The study is unexpectedly suspended or canceled.

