Background: One in ten Veterans seen in Veterans Health Administration (VHA) primary care clinics has PTSD. Individuals with PTSD are more likely to report impairments in physical functioning, including health-related limitations in climbing stairs or performing common household tasks. As an essential component of overall functioning and quality of life, physical functioning is an independent predictor of risk for adverse health outcomes, including mortality. Mechanisms underlying the association of PTSD and poor physical functioning are multifactorial, but a key contributing factor is likely persistent low levels of physical activity. Barriers to engaging in physical activity may include low perceived behavioral control for making positive long-term lifestyle changes and personal attitudes about the harms (vs. benefits) of physical activity. Those with PTSD have reduced self-efficacy for behavioral change and less ability to cope with setbacks, leading to greater difficulty with initiating and maintaining new health behaviors. Individuals with PTSD are also more likely to have ongoing pain and fatigue, which may contribute to beliefs about harmful effects of physical activity and lead to avoidance of activity. Current VHA outpatient programs are primarily focused on addressing physical activity in the context of specific medical conditions (eg, obesity or cardiovascular disease), and there is a paucity of programs specifically tailored to the unique needs of Veterans with PTSD. Development of effective programs to increase physical activity for Veterans with PTSD may therefore improve their physical functioning and represent an important contribution to VHA efforts to enhance health and recovery for this population.

Objectives/Aims: The overall objectives of this study are to develop and pilot test a novel intervention aimed at initiating and maintaining higher levels of physical activity for Veterans with PTSD.

Aim 1: Adapt graded exercise therapy (GET) and incorporate motivational interviewing and mHealth to increase physical activity and improve physical functioning for Veterans with PTSD.

Aim 2: Conduct a pilot study to examine feasibility and acceptability of the intervention for a future randomized controlled trial.

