Methods. To increase physical activity for Veterans with PTSD, this project will combine GET, motivational interviewing, and mobile health technology (mHealth) to address attitudinal and behavioral barriers particularly relevant for this group. First, we will work collaboratively with our Veteran Engagement Panel to adapt GET protocols effective for non-PTSD populations (eg, adults with chronic pain or fatigue), and incorporate motivational interviewing and mHealth. We will then pilot test the intervention in 3 consecutive groups of 6-8 participants (total n=18-24) and use concurrent mixed-methods to examine feasibility and acceptability. Quantitative measures will include recruitment (proportion enrolled out of total eligible); attendance (proportion who attend 75% of in-person visits); and retention (proportion who complete data collection post-intervention). Qualitative assessments will involve semi-structured interviews on acceptability of

intervention components (eg, session formats and topics, usability of mHealth), and barriers and facilitators to attendance. At baseline, during and post-intervention, we will also assess overall and physical functioning using Veterans RAND 36-item, 6-minute walk, and 30-second sit to stand, and collect additional data (PTSD symptoms, depression, pain, fatigue, and sleep quality) to inform a future randomized trial.

List of Abbreviations

CCDOR.....	Center for Care Delivery & Outcomes Research
CBT	Cognitive Behavioral Therapy
Co-I.....	Co-Investigator
ED.....	Emergency Department
GET	Graded Exercise Therapy
HSRD	Health Services Research and Development
IRB.....	Institutional Review Board
mHealth	Mobile Health Technology
MVAHCS	Minneapolis VA Health Care System
NIH	National Institutes of Health
PACT	Patient Aligned Care Team (VA primary care staff)
PCMHI	Primary Care Mental Health Integration
PCL-5	PTSD symptom checklist for the DSM-5
PC-PTSD-5.....	Primary Care Screen for PTSD for DSM-5
PEG	Brief 3-item Scale on Pain Intensity & Interference
PHQ-9.....	Patient Health Questionnaire-9
PI	Principal Investigator
PSQI	Pittsburgh Sleep Quality Index
PTSD	Posttraumatic Stress Disorder
PT.....	Physical Therapist
RR&D	Rehabilitation Research and Development
UMN	University of Minnesota
VA.....	Department of Veterans Affairs
VHA	Veterans Health Administration
VINCI.....	VA Informatics and Computing Infrastructure
VR-36	Veterans RAND 36-item Health Questionnaire
WRAP.....	Wearables Research and Analytics Platform

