Some elements of existing GET interventions will be directly applicable to Veterans with PTSD, due to the high prevalence of pain and fatigue symptoms among those with PTSD. However, there may be certain barriers particularly relevant to individuals with PTSD (eg, avoidance of outdoor activities due to hypervigilance) that are not addressed by current GET protocols. Additionally, past protocols required substantial clinic resources for weekly (or more frequent) in-person visits over several months, which limit feasibility for broad implementation. Extended duration of in-person visits may also reduce acceptability and uptake among those with PTSD. Therefore, GET protocols need to be adapted for Veterans with PTSD and modified to improve feasibility for implementation in outpatient settings.

2. Motivational interviewing and mobile health technology (mHealth)

Motivational interviewing has been used to address a variety of health behaviors and can be effectively delivered both in-person (individually and in groups) and by telephone.³³⁻³⁷ It focuses on eliciting personal reasons and motivations for behavioral change and engages with participants' ambivalence about change using a nonjudgmental stance. Recent studies have also shown that

mHealth (eg, wearable devices and smart-phone applications), combined with financial incentives, is effective for increasing physical activity.^{38, 39} Wearable devices enable remote collection of physical activity data, asynchronous follow-up by staff (via text messages or telephone calls), and individualized goal-setting. Thus, mHealth components may improve acceptability among participants and feasibility for implementation in busy outpatient clinical settings, due to decreased need for in-person visits. mHealth and financial incentives to increase physical activity are realistic for implementation by VHA clinical services, as they would build on existing VHA investments in mHealth (eg, for mental health treatment and smoking cessation^{40, 41}) and recent nationwide efforts to incorporate financial incentives in support of treatment for substance use disorders (ie, contingency management with financial rewards for abstinence and attendance of treatment sessions^{42, 43}).

C. Significance & Innovation

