3.0 OBJECTIVES

The overall objectives of this study are to develop and pilot test a novel intervention aimed at initiating and maintaining higher levels of physical activity for Veterans with PTSD.

Aim 1: Adapt GET and incorporate motivational interviewing and mHealth to increase physical activity and improve physical functioning for Veterans with PTSD. We will develop treatment manuals, training procedures for physical therapists (as interventionists), and processes for fidelity assessment.

Aim 2: Conduct a pilot study to examine feasibility and acceptability of the intervention for a future randomized controlled trial. We will pilot test the intervention in 3 consecutive groups of 6-8 participants (total n=18-24) and use concurrent mixed-methods to examine feasibility and acceptability. We expect 75% attendance and retention, based on results from pilot studies of group exercise interventions for PTSD (eg, retention of 76-82%).^{25, 26}

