We propose to conduct a pilot study of 3 groups with 6-8 participants each (total n=18-24). Based on our clinical and research experience with piloting group interventions, and number of participants in the active arm of recent pilot studies of group exercise interventions for PTSD,^{25, 26} we expect that 3 groups will provide sufficient data on feasibility and acceptability to inform a larger study. A control group will not be enrolled as examining efficacy is not appropriate at this stage,^{53, 54} and our main goal is to evaluate feasibility and acceptability of the active intervention. Co-Investigator [name] will be the PT interventionist conducting in-person assessments, video-conferencing sessions, and telephone calls. We will use a concurrent mixed-methods approach to assess feasibility and acceptability, and anticipate making protocol modifications as appropriate. Data on physical activity, functioning, and symptoms will also be collected, to determine feasibility of outcomes assessments for a future randomized trial.

1. Human Subjects Involvement & Characteristics.

We will screen Veterans being seen in-person or having virtual care appointments at MVAHCS primary care clinics for PTSD (ie, ≥3 on Primary Care Screen for PTSD-5) and self-reported health-related limitations in mobility (ie, climbing several flights of stairs or walking several blocks). Exclusion criteria include ongoing suicidal ideation or psychosis; medical contraindications to exercise (eg, complete paraplegia); high degree of disability (ie, impairments in ≥2 basic activities of daily living); plans to move out of the area permanently within 4 months; major neurocognitive impairment (eg, dementia), schizophrenia; acute mental health crisis within the past 3 months (requiring an ED visit or hospitalization); and routinely completing 150 minutes or more of moderate to vigorous activity per week. We will not recruit prisoners, institutionalized individuals, or children. Our goal is to conduct 3 groups of 6-8 participants each (18-24 total).

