Study participants will be asked to attend group and individual sessions during the first month, to address attitudinal and behavioral barriers to increasing physical activity. Most of these will occur by video-conferencing (see Section B). Participants will be encouraged to safely and gradually increase their daily physical activity. At the baseline in-person visit, participants will be interviewed about personal goals and motivations for increasing physical activity, beliefs about pain and fatigue related to activity, and specific barriers they have encountered in attempting to increase activity. Participants will also undergo assessments of physical functioning, PTSD and depressive symptoms, pain, fatigue, and sleep. During and after the intervention, participants will be interviewed to evaluate feasibility and acceptability of intervention components.

a. Data sources

There will be 3 sources of data for this study: 1) existing VA electronic medical record (EMR) data (from the VA Corporate Data Warehouse [CDW]) to confirm lack of medical contraindications to exercise and to capture baseline health status; 2) physical activity and sleep data collected by wearable devices and accessed via RTI's Wearables Research and Analytics Platofrm (WRAP); and 3) participant assessments, including interviews on acceptability, self-reported data (on physical activity, functioning, mental health symptoms, pain, fatigue, and sleep), 6-minute walking distance, and 30-second sit to stand test. No biological specimens will be involved. To obtain EMR information from CDW for potential participants, we will use social security numbers (SSN) and full names. Participant interviews will be audiorecorded and transcribed by the VA Health Services Research & Development (HSR&D) Transcription Core at the Salt Lake City VA. No protected health information will be shared with non-VA entities.

b. Potential risk to participants

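### Does entry on a positive PTSD screen alone undermine a pilot whose objective is worded for Veterans with PTSD?

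*Combined protocol and SAP*

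**What the plan says.** The Summary opens its background with "One in ten Veterans seen in Veterans Health Administration (VHA) primary care clinics has PTSD". In 3.0 Objectives, Aim 1 is to "Adapt GET and incorporate motivational interviewing and mHealth to increase physical activity and improve physical functioning for Veterans with PTSD". Aim 2, which covers feasibility and acceptability for a future randomised trial, does not mention PTSD, either there or in the Summary.

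Section 5.0 C.1 plans to screen Veterans at the site's "primary care clinics for PTSD (ie, ≥3 on Primary Care Screen for PTSD-5"), so it equates PTSD with a positive screen. Section 5.0 C.3 repeats the score of 3 or more as the only PTSD criterion, with "95% sensitivity and 85% specificity for PTSD diagnosis", and its lead-in speaks of PTSD symptoms. The medical record review in that section looks for exclusions.

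Table 4 schedules record diagnoses at baseline, and the PCL-5 at baseline and post-intervention. Section 5.0 C.1.a says the record data serve "to confirm lack of medical contraindications to exercise and to capture baseline health status". The symptom data have several stated uses:

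- to "collect additional data (PTSD symptoms, depression, pain, fatigue, and sleep quality) to inform a future randomized trial" (Summary, Methods);
- "to determine feasibility of outcomes assessments for a future randomized trial" (5.0 C);
- to refine how assessments are given and check data quality (5.0 C.5);
- to prompt discussion of results or referral for mental health care (5.0 C.1.c and 6.0).

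Sections 5.0 C.5 and C.6 give no PCL-5 cut-off, no definition of a recorded PTSD diagnosis and no rule for summarising PTSD status at baseline.

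**The concern.** A screen is not a diagnosis, and by quoting a specificity of 85% the protocol accepts that some positives will be false. At the low prevalence it cites, false positives among unselected screen-positives could outnumber true cases. The intervention is meant for people with PTSD: 2.0 B.1 argues that "there may be certain barriers particularly relevant to individuals with PTSD (eg, avoidance of outdoor activities due to hypervigilance") and that existing exercise protocols do not address them. If many enrollees did not have PTSD, attendance, retention and acceptability in this sample might not carry over to a trial in diagnosed patients. A reader would need the case mix to judge this, and the plan does not say how it will be shown.

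**Working it through.** **Sample size.** 3 groups × 6 = 18 and 3 groups × 8 = 24, which reproduces the stated 18-24. The plan gives no power calculation, and a single-arm feasibility pilot needs none for this point.

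**What the screen implies.** The documents state no positive predictive value (PPV), so it has to be derived. Sensitivity 0.95 and specificity 0.85 come from 5.0 C.3. The prevalence of 0.10 comes from the Summary and 2.0. All other values of the prior p are assumptions.

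PPV = 0.95p / [0.95p + 0.15(1 − p)]

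At p = 0.10: 0.095 / (0.095 + 0.135) = 0.095 / 0.230 = 0.413.

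| Prior p | PPV | Without PTSD, of 18 | Without PTSD, of 24 |
|---|---|---|---|
| 0.05 (assumed) | 0.25 | 13.5 | 18.0 |
| 0.10 (protocol) | 0.41 | 10.6 | 14.1 |
| 0.20 (assumed) | 0.61 | 7.0 | 9.3 |
| 0.30 (assumed) | 0.73 | 4.8 | 6.5 |
| 0.50 (assumed) | 0.86 | 2.5 | 3.3 |
| 0.70 (assumed) | 0.94 | 1.1 | 1.5 |

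A PPV of 0.50 needs a prior of about 14%, 0.80 about 39%, and 0.90 about 59%.

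**Which row applies.** The documents do not say. Section 5.0 C.2 relies mainly on staff referral, including integrated mental health staff, and on self-referral. Both probably raise the prior above 10%. The mobility criterion may raise it too, since 2.0 links PTSD with such limitations. The outreach route draws on an administrative list of recent positive screens and sits closest to the 10% base rate. Neither the prior on each route nor the share of participants from each is given. The prevalence and the screen's accuracy also come from different cited sources, which may not share a population or reference standard. The table shows sensitivity to the prior and does not estimate this sample.

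**Whether any planned result depends on diagnosis.**

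- Recruitment is enrolled over identified as eligible, and eligibility is set by the screen.
- Attendance is the proportion reaching 75% of visits, and retention the proportion completing post-intervention assessments. Both carry a 75% benchmark, and neither is defined by diagnosis.
- The qualitative matrices in 5.0 C.6 split by attendance and by completion, not by PTSD status.
- There is no control group and no efficacy test.

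Whether an enrollee is a true or a false positive changes no numerator, denominator or comparison in the plan.

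**Whether the case mix can be described.** Baseline PCL-5 and record diagnoses are collected, and the record data are meant to capture baseline health status. The PCL-5 distribution and a count of recorded PTSD diagnoses need no new assessment.

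**The case for a change.** The strongest case for a change is that feasibility belongs to a population. The benchmarks in 5.0 C.5 were taken from exercise pilots in PTSD, the content is shaped around PTSD, and the results are to inform a randomised trial. Disclosing the definition in the methods does not stop a report from speaking loosely of Veterans with PTSD. Fixing the PCL-5 cut-off and the record definition beforehand would also prevent a choice made after seeing 18-24 people, at the cost of a few sentences.

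Part of this stands. No diagnostic step exists, no summary rule is written, and readers will want the case mix. The rest is weaker. An overclaim in a later report is a prediction, not a fault in this text: the objective never says diagnosed, Aim 2 does not mention PTSD, and the eligibility section refers to symptoms. A cut-off chosen late could bias little, because no planned result uses one and the full PCL-5 distribution can be shown without any. A recorded diagnosis and a PCL-5 score would describe the sample without confirming PTSD, so elaborate rules for reconciling them would add little at this size. The counts in the table are expected true non-cases; they do not predict how many participants would lack a recorded diagnosis or fall below a PCL-5 cut-off.

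**Conclusion.** No change to the plan is needed. Entry by a routinely administered screen is deliberate and disclosed, and it suits a pilot meant to resemble referral in ordinary clinic care. What remains is the unwritten layout of a baseline table, which an analyst would fill sensibly from data already scheduled: describe participants as screening positive for PTSD, show the baseline PCL-5 distribution and count those with a recorded PTSD diagnosis. That is routine reporting.

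The effect on the planned results is nil: the sample of 18-24, the 75% benchmarks and the comparisons stay as they are. The effect on interpretation cannot be sized from the documents. The PPV runs from 25% to 94% over priors of 5% to 70%, and the 41% at the protocol's 10% applies only to unselected screen-positives. The conclusion assumes that the scheduled PCL-5 and record diagnoses are collected and reported as baseline descriptors. A future trial that required a diagnosis would have to use those descriptors to judge how far the pilot's results transfer.
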